3.1 General Considerations

3.1.1 Statistical Software

All statistical analyses will be performed using SAS (SAS Institute, NC, USA) or R (R Foundation for Statistical Computing, Vienna, Austria).

3.1.2 Summary Statistics

Data will be summarized with respect to disposition, demographics, pre-treatment characteristics, safety outcomes, tolerability, and TMS, TTNCS, pharmacologic, clinical, and quality of life outcomes. Summary statistics for continuous variables will include the number of subjects, the mean, median, standard deviation, and range. For categorical data, summaries will include counts and percentages.

3.1.3 Precision

Results will generally be reported to 3 significant figures. Percentages will generally be reported to 0.1 percentage points. P-values will be reported to two digits when greater than or equal to 0.095, to three digits when greater than or equal to 0.00095 and less than 0.095, and as <0.001 for all smaller values.

3.2 Study Endpoints

3.2.1 Pharmacodynamic Endpoints

The primary pharmacodynamic endpoint is the change in RMT estimated from single-pulse TMS measurements made before treatment, after 4 weeks of treatment, and then again after a 4-week washout.

Secondary pharmacodynamic endpoints include change in the following measures made before treatment, after 4 weeks of treatment, and then again after a 4-week washout.

TMS measures:

- Maximum MEP amplitude (as a percentage of maximum CMAP),
- Slope of the input/output curve describing the relationship between stimulus strength (in percent of maximum stimulator output) and motor evoked potential (MEP) amplitude (in mV),
- Cortical silent period (CSP).

TTNCS measures:

- Strength duration time-constant (SDTC),
- Depolarizing and hyperpolarizing electrotonus at 90 to 100 ms (TEd(90-100 ms) and TEh(90-100 ms)),
- Recovery cycle measures of relative refractory period (RRP), superexcitability, and subexcitability, and
- Compound motor action potential (CMAP).

Exploratory pharmacodynamic measures include: intracortical facilitation (ICF) by TMS; rheobase, TEd(40-60 ms), TEh(10-20 ms), TEd(peak), subexcitability after second pre-pulse, and stimulus for 50% maximum response assessed by TTNCS.

3.2.2 Clinical and Quality of Life Endpoints

Exploratory clinical and quality of life endpoints include change in the following measures made before treatment, after 4 weeks of treatment, and then again after a 4-week washout.

Clinical measures:

- ALS Functional Rating Scale-Revised (ALSFRS-R) total score,
- Slow vital capacity (SVC),
- Abductor pollicis brevis (APB) muscle strength by hand-held dynamometry (HHD),
- Muscle cramping frequency and pain, and
- Fasciculation occurrence and interference with daily life.

Quality of Life measures:

- Physical and mental summary scores from the RAND-36 Health Survey.

3.2.3 Safety Endpoints

The following safety endpoints will be evaluated:

- Proportion of participants experiencing and number of unique events of each type of TEAE and serious TEAE classified by MedDRA system organ class and preferred term,
- Proportion of participants experiencing and number of unique events of TEAEs classified by seriousness, severity, relatedness to study drug, relatedness to TMS and TTNCS procedures, action taken with study drug, action taken with TMS/TTNCS, and outcome, summarized across all MedDRA terms,
- Instances of treatment-emergent and clinically significant laboratory abnormalities classified by assay, whether the abnormality is below or above the normal range,
- Mean change from baseline in weight
- Proportion of participants experiencing treatment-emergent and clinically significant ECG abnormalities by type of finding
- Proportion of participants experiencing treatment-emergent and clinically significant physical examination findings by body system
- Proportion of participants experiencing treatment-emergent neurological examination findings by type of finding

Reported proportions will use as their denominator all participants in the Safety and Tolerability sample (see Section 3.5 below).

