8.1.7. Final Safety Visit

Subjects who discontinue study drug early are encouraged to come in for a Final Safety Visit. The following will be performed:

- Perform physical and neurological examinations
- Measure vital signs and weight
- Perform 12-lead ECG
- Collect blood samples for clinical laboratory assessments including:
 - Hematology and differential panel
 - Blood chemistry panel
 - Urine pregnancy test (for woman of childbearing potential [WOCBP])
- Collect blood for plasma mexiletine level and plasma for NEALS biorepository
- Administer ALSFRS-R questionnaire
- Administer RAND-36
- Perform APB testing by HHD
- Perform SVC
- Perform TMS/TTNCS
- Review returned Muscle Cramping/Fasciculations Diary
- Review and document concomitant medications and therapies
- Assess and document AEs
- Check study drug compliance and collect dosing diary
- Perform study drug accountability and collect all unused study drug and empty containers
- Perform Blindness Questionnaire and Exit Survey

All subjects who discontinue study drug early will be encouraged to complete follow-up per study protocol under the intent-to-treat (ITT) principle. If they are unable to return for in-person visits, the scheduled in-person visits can be replaced by Telephone Interviews. Telephone Interviews will occur at the same intervals as regularly-scheduled Study Visits (Weeks 4 and 8). The first Follow-up Telephone Call will occur at the next scheduled study visit. Subjects who withdraw consent will also be asked to come in for a Final Safety Visit.

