3.2.4 Tolerability Endpoint

Participants will be judged tolerant of study drug if they reached their target dose and remain on study drug until planned discontinuation. Tolerability will be summarized separately for freedom from intolerance due to an AE and intolerance for any reason, in each case as the proportion of participants in a treatment group who are tolerant of study drug. The proportion of participants who report willingness to participate in a future trial that used TMS and TTNCS on the Exit Survey will be reported. Reported proportions will use as their denominator all participants in the Safety and Tolerability sample (see Section 3.5 below).

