3.5 Analysis Samples

The following analysis samples will be used for testing safety, tolerability, and efficacy endpoints:

- Safety and Tolerability (ST) Sample: ALS participants who are eligible, randomized, and take at least one dose of study drug, classified according to the actual treatment received. Observations made after premature permanent discontinuation of study drug are included in this sample, should such participants remain on study.
- Efficacy Modified Intent-to-treat (mITT) Sample: ALS participants who are eligible, randomized, and take at least one dose of study drug, classified according to their randomized treatment assignment. Observations made after premature permanent discontinuation of study drug are included in this sample, should such participants remain on study.

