3.8.2 Safety Labs

The absolute level and the absolute change from baseline for each safety laboratory assay will be summarized as means, standard deviations, medians, and ranges at each visit by treatment group. The proportion of participants with abnormal and clinically significant safety lab levels will be summarized by treatment group by visit and at any post-baseline visit.

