3.8.4 Physical and Neurological Examinations

The proportion of participants with any treatment-emergent and clinically significant physical or neurological findings will be summarized by treatment group.

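### SAP 3.2.3 divides ECG and examination proportions by the whole Safety and Tolerability sample, so dosed participants never assessed afterwards are in effect counted as having no abnormality

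*SAP*

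**What the plan says.** SAP 3.2.3 lists the safety endpoints. Those expressed as proportions are treatment-emergent adverse events, ECG abnormalities, physical examination findings and neurological examination findings. The laboratory endpoint in that list is a count: "Instances of treatment-emergent and clinically significant laboratory abnormalities classified by assay". The section closes with "Reported proportions will use as their denominator all participants in the Safety and Tolerability sample".

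SAP 3.5 defines that sample as "ALS participants who are eligible, randomized, and take at least one dose of study drug, classified according to the actual treatment received". No assessment after the first dose is required.

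Three other sections bear on the point:

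- SAP 3.8.2: the proportion with abnormal and clinically significant laboratory levels "will be summarized by treatment group by visit and at any post-baseline visit". It states no denominator of its own.
- SAP 3.8.4: "The proportion of participants with any treatment-emergent and clinically significant physical or neurological findings will be summarized by treatment group". It does not ask for the number examined.
- SAP 3.2.4: "The proportion of participants who report willingness to participate in a future trial that used TMS and TTNCS on the Exit Survey will be reported". The same whole-sample denominator sentence follows.

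After the first dose, laboratory tests and examinations take place only at Week 4, Week 8 or the Final Safety Visit (Protocol Table 1, 7.1.2 and 7.1.5). An ECG is also scheduled 1 to 2 hours after the first dose (Protocol 8.1.3). For participants who stop study drug early and cannot come back, "the scheduled in-person visits can be replaced by Telephone Interviews" (Protocol 8.1.7). Protocol 5.6 says those calls include the ALSFRS-R, adverse events and concomitant medications.

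**The concern.** A participant who took one dose and had no later examination cannot show an abnormality but is still in the denominator. The table treats that person exactly like someone examined and found normal. Nothing elsewhere in the SAP corrects this. SAP 3.1.2 asks only for counts and percentages for categorical data. SAP 3.8.2 and 3.8.4 have no rule for a missing assessment, and SAP 3.7.7 deals with missing data for the mixed model.

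The by-visit laboratory proportions are the most exposed, if the SAP 3.2.3 rule governs them. Someone seen only at a Final Safety Visit and then followed by telephone has no Week 4 or Week 8 sample. The SAP assigns that visit to a scheduled visit only for the model in SAP 3.7.1.

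The ECG is a partial case. Almost everyone dosed should have the Day 1 reading, but under SAP 2.6 it follows a single 150 mg capsule in both active arms. It says nothing about exposure at the target dose.

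What is at stake is the reading of the safety tables. Protocol 13.8 bases the dose to carry forward on several rates, clinical abnormalities among them. A proportion that falls because fewer people were examined could be mistaken for a cleaner safety result.

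**Working it through.** **Inputs from the documents**
- 60 participants randomized 1:1:1, so N = 20 per arm; up to 10% loss to follow-up (SAP 3.4).
- Intolerance in the earlier ALS trial: 5% at 300 mg/day and 32% at 900 mg/day (Protocol 2.1.3.2).
- An 80% probability of seeing at least one instance of an event with a 4% rate in 40 exposed, or an 8% rate in a single dose arm (Protocol 13.7).

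**Assumptions.** The documents give no abnormality rate and no non-assessment rate. Let r be the rate among those assessed (10% and 20% are used) and m the number in an arm never assessed after dosing.

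**1. The plan's own safety figure.** No figure is given for the denominator rule itself; the nearest is the 80%.
- 1 − 0.96^40 = 80.5%
- 1 − 0.92^20 = 81.1%

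Both agree with the stated 80%, but they need everyone to be observed. If only 18, 16 or 14 of 20 are assessed, the chance of seeing an 8% laboratory or examination event is 77.7%, 73.7% or 68.9%. Changing the denominator does not recover that loss; printing the number assessed makes it visible.

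**2. Dilution.** Expected reported proportion = r × (N − m)/N.

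| m of 20 unassessed | r = 10% | r = 20% |
|---|---|---|
| 0 | 10% | 20% |
| 1 | 9.5% | 19% |
| 2 | 9% | 18% |
| 4 | 8% | 16% |
| 6 | 7% | 14% |

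The relative loss is m/20. With those assessed as the denominator, the expected value stays at r.

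**3. At the planned loss.** 10% of 60 is 6 participants; take r = 20% in every arm.
- Spread 2/2/2: 0.20 × 18/20 = 18% in each arm, so no spurious difference.
- All 6 in one arm: 20%, 20% and 0.20 × 14/20 = 14%.

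**4. If non-assessment followed stopping.** Let f be the share of stoppers never assessed. As an outer illustration, use the earlier trial's 5% and 32% as stopping rates, with r = 20% in both arms. The reported rates are 0.20 × (1 − 0.05f) and 0.20 × (1 − 0.32f).

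| f | 5% stopping | 32% stopping |
|---|---|---|
| 0 | 20% | 20% |
| 25% | 19.8% | 18.4% |
| 50% | 19.5% | 16.8% |
| 100% | 19.0% | 13.6% |

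At f = 100% the ratio is 13.6/19.0 = 0.72 although the true rates are equal.

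**5. Exit Survey.** If 2 of 20 do not complete it and all 18 completers are willing, SAP 3.2.4 gives 18/20 = 90%, not 100%.

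**The case against.** A reader might infer that every safety proportion is biased and that the rule favours the less tolerated dose. The documents do not support either inference.

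- **Scope.** The whole-sample denominator is right for treatment-emergent adverse events, which the telephone calls also collect. The laboratory endpoint in SAP 3.2.3 is a count. SAP 3.8.2 names no denominator, and a by-visit proportion can reasonably be read as a proportion of those tested at that visit.
- **Stopping is not non-assessment.** SAP 2.4 keeps stoppers on the normal schedule. SAP 2.8 provides a Final Safety Visit for those who stop before Week 4, and under Protocol 8.1.7 it includes laboratory tests, an ECG and both examinations. Telephone contact is for those who cannot return, and Protocol 7.1.2 allows other arrangements for laboratory testing.
- **Size.** The 32% is intolerance at 900 mg/day, which is not an arm here, and only some of those patients stopped. At 20 per arm, 5 points is one participant.
- **Decision.** Protocol 13.8 also counts early termination of study drug and withdrawal, and sets no absolute criteria. An arm with many stoppers is marked down for that directly.
- **Visibility.** SAP 3.1.2 requires the number of subjects for continuous summaries, so the number with a laboratory value at each visit should be visible. Disposition and tolerance are reported by arm. Clinically significant abnormal findings are also adverse events under Protocol 14.1.1.
- **The alternative has its own assumption.** Using only those assessed supposes that the unassessed resemble them.

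The points on scope, stopping, size and decision stand, and they limit the claim. The visibility point helps for laboratory values but not for examination findings, and an abnormality nobody tested for cannot be reported as an adverse event. The last point is the reason to print both numbers rather than to keep the present rule.

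**Conclusion.** The concern holds in limited form. For ECG, physical examination and neurological examination proportions, the stated rule counts unassessed participants as free of abnormality. It does the same to the by-visit laboratory proportions only if SAP 3.2.3 is taken to govern SAP 3.8.2, which the SAP leaves open. It treats a missing Exit Survey as not reporting willingness.

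The relative loss is m/20 per arm: one percentage point for each unassessed participant at an assumed rate of 20%, half a point at 10%. A difference between arms needs unequal non-assessment. The documents make that possible but do not establish it, so the 19.0% against 13.6% contrast is an extreme illustration and not a forecast. These are descriptive summaries in SAP 3.8; the primary RMT analysis is untouched.

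**What to change.** Amend the SAP as follows.

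- **3.2.3 and 3.2.4:** keep the Safety and Tolerability sample as denominator for treatment-emergent adverse events and for tolerance of study drug.
- **3.2.3, 3.8.2 and 3.8.4:** for laboratory, ECG, physical and neurological examination proportions, use participants with at least one post-dose assessment of that type. In by-visit tables, use those assessed at that visit. Show ECG readings after Day 1 separately from the Day 1 reading.
- **All of these tables:** print the number assessed over the number in the Safety and Tolerability sample, by arm.
- **3.2.4, Exit Survey:** use those who completed the survey and show how many did not.

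The cost is SAP wording and table shells; no new data are needed. Denominators will differ between tables. The assessed-only rate assumes that the unassessed resemble the assessed, and printing both numbers lets the reader judge that assumption and see any imbalance between arms.

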3.2.4 Tolerability Endpoint

Participants will be judged tolerant of study drug if they reached their target dose and remain on study drug until planned discontinuation. Tolerability will be summarized separately for freedom from intolerance due to an AE and intolerance for any reason, in each case as the proportion of participants in a treatment group who are tolerant of study drug. The proportion of participants who report willingness to participate in a future trial that used TMS and TTNCS on the Exit Survey will be reported. Reported proportions will use as their denominator all participants in the Safety and Tolerability sample (see Section 3.5 below).

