6.2. Treatments Administered

The three treatment arms include placebo, mexiletine 300 mg/day, and mexiletine 600 mg/day. Mexiletine or the matching placebo will be taken orally as a capsule. Subjects must be able to

swallow oral medication at the Baseline Visit and expected to be able to swallow the capsule throughout the course of the study to be eligible for enrollment. The capsules must not be opened and mixed with food/drink or any gastrostomy feedings. Study drug capsules must be taken with solid food or antacids. It may not be taken with a liquid diet.

Capsules will contain 150 mg of either placebo or mexiletine and will be administered concurrently from two bottles containing 60 capsules each. Study subjects will be titrated up to the appropriate dosage level over the course of 7 days (see Table 5. Study Drug Titration Schedule). After the titration period, the subject will continue at the target dosage level of 2 capsules twice a day until the Week 4 Visit. Mexiletine and placebo will be packaged in kits. Each subject is expected to utilize one kit during study participation. Additional drug kits will be shipped to each site, as needed based on enrollment.

Mexiletine or placebo will be started at the Baseline Visit and continue treatment until the Week 4 Visit. The day that a subject starts treatment with study drug will be designated as Day 1. All subsequent visits must be scheduled from the Baseline Visit, not the date of their last assessment. The first dose of study treatment will be administered in the clinic by authorized site personnel and will be observed in clinic for 1-2 hours post-dose.

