6.2.1. Dosage Initiation/Escalation

Given the gastrointestinal (GI) side effects to taking mexiletine, a titration approach was chosen for this study. Mexiletine will be supplied as 150 mg capsules in bottles containing 60 capsules. Study drug kits will contain two bottles labeled 1 and 2. Each participant will start with 1 capsule a day, the first dose taken at the Baseline Visit and the second taken in the am from bottle 1 for 2 days (Day 1 – 2). Subjects will follow the titration schedule illustrated below in Table 5 until the full study dosage level is reached at Day 7. After initial titration, subjects will take 2 capsules of study drug in the morning and in the evening. One capsule will be taken from each bottle labeled with a 1 in the morning and evening until the Week 4 Visit. Each bottle is good for 4 weeks of dosing.

Table 5. Study Drug Titration Schedule

Number of capsules per bottle per day – Bottle 1 and 2

	Day 1-2	Day 3-4	Day 5-6	Day 7
Bottle #1	1 QD	1 BID	1 BID	1 BID
Bottle #2	-	-	1 Q AM	1 BID

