6.4. Study Drug Adjustments, Dosage Reductions and Suspensions

Any dosage adjustment including the reason for and dates of adjustment will be documented in the CRF for each subject requiring this manipulation. The Site Investigator or licensed physician Sub-Investigator has the option of reducing or temporarily stopping the study drug for AEs thought to be related to the study drug or any other reason during the trial (the reason for, and dates of suspension or dose reduction must be documented). If the adverse event is mild or moderate, the dosage may be reduced until the event improves (See Table 6. Study Drug Reduction Schedule). The Site Investigator may then choose to resume the higher dosage or maintain the subject at a reduced dosage. If the event is serious or life threatening, and deemed to be drug related, the study drug should be discontinued immediately. Study subjects may remain off the study drug permanently, until the condition improves or they may resume on a reduced dosage, as advised by the Site Investigator. Subjects may not resume study drug after a suspension that is longer than 10 days. Any resumption of drug after a suspension requires approval from the Medical Monitor. All adverse events will be followed for resolution or 28+5 days after stopping study drug.

Table 6. Study Drug Reduction Schedule: Number of capsules per bottle per day

	Day 1-2 Dose Reduction	Day 3-4 Dose Reduction	Day 5-6 Dose Reduction
Bottle #1	1 BID	1 BID	1 Q AM
Bottle #2	1 Q AM	-	-

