7.1.6. Adverse Events

Adverse events will be documented at each study visit, including the Screening Visit once the informed consent form has been signed by the subject. Information on adverse effects of study medication and on inter-current events will be determined at each visit by direct questioning of the subjects, clinical examination, review of concomitant medications, vital signs and laboratory test results. Tolerability will be determined by the ability to complete the study on the assigned treatment at the assigned dose. Subjects on a dose reduction are considered intolerant. Side effects that would not be tolerable in a drug chronically administered are of particular interest. Given the severity of the disease, some significant side effects might be tolerated.

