2.6 Treatment Administration

Study drug will be orally self-administered from 2 bottles containing either 150 mg capsules of mexiletine or placebo capsules matched for size, color, and presentation. All participants will take one capsule for bottle #1 at their baseline visit (day 1) and on the morning of day 2, one capsule from bottle #1 BID from day 3 until their week 4 visit, one capsule from bottle #2 on the morning of days 5 and 6, and one capsule from bottle #2 BID from day 7 until their week 4 visit.

In the placebo arm, bottles #1 and #2 will contain placebo capsules, and the dosage of mexiletine will be 0 mg/day throughout their participation. In the 300 mg/day arm, bottle #1 will contain 150 mg capsules of mexiletine and bottle #2 will contain placebo. Dosage of mexiletine will be titrated as follows: 150 mg at their baseline visit, 150 mg on the morning of day 2, and 150 mg BID (300 mg/day) from day 3 until their week 4 visit. In the 600 mg/day arm, bottles #1 and #2 will contain 150 mg capsules of mexiletine. Dosage of mexiletine will be titrated as follows: 150 mg at their baseline visit, 150 mg on the morning of day 2, 150 mg BID (300 mg/day) on days 3 and 4, 300 mg QAM and 150 mg QPM (450 mg/day) on days 5 and 6, and 300 mg BID (600 mg/day) from day 7 until their week 4 visit.

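### SAP 3.2.4 puts no condition on the dose held after target, so a participant who finishes on a reduced dose counts as tolerant, although protocol 7.1.6 classes that participant as intolerant

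*SAP*

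**What the plan says.** SAP 3.2.4 gives the rule for the tolerability endpoint: "Participants will be judged tolerant of study drug if they reached their target dose and remain on study drug until planned discontinuation". The result is reported as a proportion of each treatment group, once for intolerance due to an adverse event and once for intolerance for any reason. SAP 3.9.2 repeats the summary and adds no dose condition.

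Protocol 7.1.6 defines tolerability differently: "Tolerability will be determined by the ability to complete the study on the assigned treatment at the assigned dose". The next sentence reads "Subjects on a dose reduction are considered intolerant".

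Protocol 6.4 allows reduction for adverse events or for any other reason, with a stepwise schedule in Table 6. After improvement, "The Site Investigator may then choose to resume the higher dosage or maintain the subject at a reduced dosage".

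Two other protocol sections, 7.1 and 13.1, link tolerability to treatment discontinuations and do not mention reductions. The opening section of the SAP says that it supplements the protocol and that it prevails where the two differ on matters of analysis.

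The dose target is described in two ways. Protocol 6.2 gives it in capsules: "the subject will continue at the target dosage level of 2 capsules twice a day until the Week 4 Visit". Protocol 6.2.1 has titration run "until the full study dosage level is reached at Day 7". SAP 2.6 gives it in mg by arm: "In the 300 mg/day arm, bottle #1 will contain 150 mg capsules of mexiletine and bottle #2 will contain placebo", with that arm on "150 mg BID (300 mg/day) from day 3 until their week 4 visit".

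**The concern.** The two definitions classify the same person differently. Someone who reaches target, is reduced, and is still taking the reduced dose at the Week 4 visit meets both conditions of SAP 3.2.4 but is intolerant under protocol 7.1.6. Because the SAP governs analysis, the looser rule would decide the reported figure.

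What is at stake is how the 600 mg/day arm is described. The protocol summary names tolerability of the high dose among the reasons for choosing the doses, and SAP 2.2 makes tolerability a secondary objective. The protocol describes mexiletine's common reactions as dose-related and reversible on lowering the dose (2.2.3), so reductions after target are foreseeable. A tolerant proportion that includes people who could not stay on 600 mg/day would overstate tolerance of that dose.

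**Working it through.** The plan states no figure to reproduce. The check applies both definitions to one case, then works out the weight of one participant.

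**The case.** Target is reached on Day 7 (protocol 6.2.1), the dose is later reduced and kept reduced (6.4), and study drug continues to planned discontinuation.

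- SAP 3.2.4, target reached: yes.
- SAP 3.2.4, on study drug until planned discontinuation: yes. Result: tolerant.
- Protocol 7.1.6, completed at the assigned dose: no; on a dose reduction: yes. Result: intolerant.

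A participant who never reached target is not tolerant under either text, so the conflict covers only reductions made after target.

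**Daily dose at each Table 6 step.** Capsule counts come from Table 6 and bottle contents from SAP 2.6; each active capsule is 150 mg.

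| Step held to the end | Capsules/day (bottle 1 + bottle 2) | 600 mg arm | 300 mg arm | Placebo |
|---|---|---|---|---|
| None (full) | 2 + 2 = 4 | 4 × 150 = 600 mg | 2 × 150 = 300 mg | 0 |
| First | 2 + 1 = 3 | 3 × 150 = 450 mg | 2 × 150 = 300 mg | 0 |
| Second | 2 + 0 = 2 | 2 × 150 = 300 mg | 2 × 150 = 300 mg | 0 |
| Third | 1 + 0 = 1 | 1 × 150 = 150 mg | 1 × 150 = 150 mg | 0 |

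- 600 mg arm: all three steps are reductions, whether counted in capsules or in mg.
- 300 mg arm: the third step is a reduction on either basis. The first two drop only placebo capsules, so they are reductions in capsules but not in mg.
- Placebo: a reduction exists only in capsules.

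The same ambiguity affects whether target was reached. In mg, the 300 mg arm is at 300 mg/day from day 3; in capsules, no arm is at target before Day 7.

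**Weight of one participant.** About 60 are randomized 1:1:1 (protocol 5.1), so 60/3 = 20 per arm and 1/20 = 5 percentage points. The documents give no expected number of reductions. For an assumed 0, 1, 2 or 3 participants ending on a reduction, the arm's proportion is higher by 0, 5, 10 or 15 points.

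**The case against.** The strongest reply is that the SAP is silent rather than contradictory. It supplements the protocol, and it uses the word intolerance without defining it, so protocol 7.1.6 could be read as filling the gap. That reading is possible but not secure. SAP 3.2.4 is worded as a complete rule for who is judged tolerant, and an analyst programming it as written would count the reduced-dose participant as tolerant.

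A second reply is that protocol 7.1 and 13.1 look only at discontinuations, which is closer to the SAP. This stands in part: the protocol is not uniform, and the documents do not establish that 7.1.6 must prevail. But neither section says that a reduction counts as tolerated, and 7.1.6 is the only text that addresses reductions. It is not a clean standard either. A 300 mg participant who drops only placebo capsules is still at the assigned dose in mg, yet is on a Table 6 reduction.

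A third reply is that the effect is small and visible elsewhere. That largely stands. No test is specified for the proportion, adverse-event-driven reductions appear under action taken with study drug (SAP 3.2.3 and 3.8.1), and protocol 13.8 does not list reductions among the inputs to dose selection.

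A reader might also infer that the compliance summary would hide such participants because their intake stays above 80%. The documents do not support that as a general claim. Planned capsules for Days 1 to 28 are 2×1 + 2×2 + 2×3 + 22×4 = 100. A reduction from Day 21 through to the last step gives 12 + 14×4 + 2×3 + 2×2 + 4×1 = 82, or 82%, but only with a Day 29 visit. Protocol 8.1.5 allows Days 29 to 32 with the last dose the night before. At a Day 30 visit the figure is 83/104 = 79.8%, and at Day 32 it is 85/112 = 75.9%. The 80% limit belongs to protocol 6.7; SAP 3.9.2 reports a percentage with no cut-off.

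**Conclusion.** The mismatch is real and its severity is minor. Read literally, SAP 3.2.4 reports as tolerant a participant who reached target and finished on a reduced dose, whereas protocol 7.1.6 reports that participant as intolerant. Each one adds about 5 points to an arm of about 20. The total is unknown and is zero if nobody ends on a reduction.

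This rests on two assumptions: that remaining on study drug is taken at face value and does not imply the target dose, and that arms are close to 20.

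A reader might infer that the dose carried forward, or the primary analysis, is compromised. The documents do not support either. The tolerant proportion is descriptive, reductions are not among the listed selection inputs, and the resting motor threshold analysis does not use this definition.

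**What to change.** Before unblinding, amend SAP 3.2.4 so that tolerance requires reaching target and being on the full assigned study drug at planned discontinuation, with a participant then on a dose reduction not counted as tolerant of the assigned dose. Reconcile protocol 7.1.6, 7.1 and 13.1 with that wording. The change concerns classification only and alters nothing about how participants are dosed.

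State whether target and reduction are counted in capsules or in mg. Capsules match protocol 6.2 and give one blinded rule for all arms, but class some 300 mg participants as intolerant while they still take 300 mg/day. Counting in mg avoids that but has no meaning on placebo.

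Report by arm the number with any dose reduction, including temporary ones, because the documents do not clearly classify a participant who was reduced and then returned to full dose.

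The cost is wording and one extra table row. Protocol 6.4 already has dose adjustments, reasons and dates recorded on the CRF. The tolerant proportion may be slightly lower, by about 5 points per participant who ends on a reduction.
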